**Part 2 (Dose Expansion):**

Histologically or cytologically proven advanced NSCLC whose tumours are KRAS-mutated and where the disease has progressed after a chemotherapy and immunotherapy regimen (at least two prior lines of standard therapy), advanced TNBC where the disease has progressed after having received at least one line of prior systemic treatment for advanced disease and advanced CRC whose tumours are RAS mutated and where the disease has progressed after at least two prior lines of standard therapy.

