Efficacy parameters:	
Tumour response:
 
 
• ORR (primary efficacy endpoint);
 
• DCR; PFS; OS; TTP; TTR; DOR (secondary efficacy endpoints) (only Part 2).
 

Pharmacokinetic parameters:	PK parameters of OMO-103: AUC; C min ; C max ; t max ; t 1/2 .
PD parameters:	Circulating human ADA to OMO-103; Ki67 and CC3 by IHC; Immune infiltration by IHC (CD3, CD4/CD8, PD-1/ PD-L1) and others to be determined; Multiplex assay from biopsies (e.g., MYC-

expression levels); Cytokines and other PD biomarkers for the purpose of an optional genetic analysis and for target validation; PBMC and immune characterisation blood samples only during Part 2 (Dose Expansion).

**Statistical methods:**Sample Size

The sample size is determined based on clinical rather than statistical considerations. For the dose escalation part, up to 24 patients are anticipated to be recruited. The number of patients in this study is consistent with Phase 1 dose finding studies. In Part 2, at least 3 parallel groups of patients with advanced NSCLC, TNBC and CRC will be treated. Approximately 18 patients will be enrolled in each group in Part 2.

General Considerations

In general, all data will be summarised using appropriate descriptive statistics by per dose cohort and for the expansion groups where applicable. Summary tabulations will be presented that display the number of patients (N), number of observations, mean, SD, median, minimum, and maximum for continuous variables, and the number and percent (of non-missing values) per category for categorical data by absolute and relative frequencies.

Unless indicated otherwise, summary statistics will be reported for observed data only. Missing data will not be imputed. If a baseline value is missing, no change from baseline will be calculated.

Baseline is defined as the last assessment before the start of IMP administration.

Safety data will be reviewed continuously and integrated with PK and PD data at the end of dose escalation in order to determine the dose to be administered during the dose expansion part of the study. The same data will be integrated at the conclusion of the study in order to determine the RP2D to be used in future trials of OMO-103.

Interim Analysis

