2 STUDY OBJECTIVES

Part 1 – Dose Escalation

Primary Objective:

- To evaluate the safety and tolerability of OMO-103 in adult patients with advanced solid tumours.

Secondary Objectives:

- To establish and confirm the recommended Phase 2 dose (RP2D) and dosing regimen of OMO-103 for further development.
- To characterise the pharmacokinetics (PK) of OMO-103.
- To evaluate preliminary anti-tumour activity in the dose escalation part.
- To assess the development of human anti-drug antibodies (ADA) to OMO-103.

Part 2 – Dose Expansion

Primary Objective:

- To assess the preliminary anti-tumour activity of OMO-103 monotherapy as measured by progression free survival (PFS) according to standard criteria (Response Evaluation Criteria in Solid Tumours [RECIST] v1.1 [Eisenhauer 2009]).

Secondary Objectives:

- To confirm the RP2D and dosing regimen of OMO-103 for further development.
- To assess the type, incidence, severity, timing, seriousness, and relatedness of adverse events (AEs) and laboratory abnormalities.
- To characterise the PK of OMO-103.
- To assess other efficacy parameters in patients with advanced solid tumours including disease control rate (DCR), objective response rate (ORR), overall survival (OS), time to progression (TTP), time to response (TTR) and duration of response (DOR) by RECIST v1.1.
- To assess the development of human ADA to OMO-103.
- To evaluate the effect of OMO-103 on Quality of Life (QoL) measured by the Quality of Life questionnaire.

Exploratory (Both Parts 1 and 2):

- Evaluation of potential biomarkers.
- Myc expression levels.

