10 STATISTICAL METHODS

10.1 GENERAL PRINCIPLES

- All statistical methods will be based on the International Conference on Harmonisation (ICH) E9 document “Statistical Principles for Clinical Trials”.
- All data collected will be presented within data listings.
- Generally, data listings will be sorted by subject and by period/regimen where appropriate.
- Generally, data will be summarised by period/cohort. Baseline data will be summarised overall. The format of the summaries is defined in the shells at the end of this document.
- Repeated visits will be denoted with ‘RPT’. Unscheduled visits will be denoted with ‘UNS’.
- In summary and analysis tables of continuous variables, standard descriptive statistics (N [number within analysis set, or group, or subgroup], n [number of observations included in analysis], mean, standard deviation [SD], median, minimum and maximum) will be presented. Least squares means (LSMean) and 95% confidence intervals (CI) will be presented in the

statistical analysis outputs as appropriate. For PK summaries, geometric mean and coefficient of variation (%CV) will also be used to summarise the data.

- Unless otherwise specified, the minimum and maximum statistics will be presented in summary tables to the same number of decimal places as the original data. The mean, median, LSMeans, and CI will be presented to one more decimal place than the original data. SD will be presented to two more decimal places than the original data.
- Derived PK parameters and concentration data listings and summaries will be presented to 3 significant figures (with the exception of CV%, which will be presented to 1 decimal place). The ratio of the geometric LSMeans and its associated confidence interval will be presented to 2 decimal places.
- In summary tables of categorical variables, the number of non-missing observations by category will be presented along with percentages. Unless otherwise specified, the denominator for each percentage will be the number of non-missing observations.
- All percentages will be presented to one decimal place.
- All plots will use a linear time scale for the nominal times of the visits and will be labelled by time point.

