10.4 MISSING DATA

No methods to account for missing safety data will be used.

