11.5.2 Laboratory Data

Routine safety clinical laboratory tests will be carried out at Screening.

The laboratory parameters required for this study are listed in section 9.2.1.

Laboratory safety data listings will be presented in two ways:

- Out of range values - any values that fall outside of the normal/alert ranges based on the reference ranges provided by the local/central laboratory (presented in listing format within the data summaries)
- All safety laboratory data (including physician's review (Normal, Abnormal-NCS, Abnormal-CS)) with any out of range values flagged (presented within the data listings).

Pregnancy test, post-menopausal assessment and any unplanned laboratory parameters will also be listed.

If there are no further parameters databased other than those specified in section 9.2.1 then the 'Other Laboratory Data' listings should display, '*No other laboratory parameters to report.*'

Laboratory data will be listed using the Safety Set.

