16.2.9 Individual Laboratory Safety Measurements

Listing 16.2.9.1	Biochemistry Data	Safety Set
Listing 16.2.9.2	Haematology Data	Safety Set
Listing 16.2.9.3	Urinalysis Data	Safety Set
Listing 16.2.9.4	Summary of Anti-drug antibodies (ADA) to OMO-103	Safety Set
Listing 16.2.9.5	Other Laboratory Data	Safety Set

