Subject	Visit/ Time Point	Sample Date/Time	Sample ID	Parameter	Result	Unit	Flag	Normal Range	
								Low	High
xxx	xxxxxx	xxxxxxxxxx	xxxxx	xxxxxxx	x.xx	xxx	x	x.x	x.xx
				xxxxxxx	x.xx	xxx	x	x.x	x.xx
				xxxxxxx	x.xx	xxx	x	x.x	x.xx
				xxxxxxx	x.xx	xxx	x	x.x	x.xx
	xxxxxx	xxxxxxxxxx	xxxxx	xxxxxxx	x.xx	xxx	x	x.x	x.xx
				xxxxxxx	x.xx	xxx	x	x.x	x.xx
				xxxxxxx	x.xx	xxx	x	x.x	x.xx
				xxxxxxx	x.xx	xxx	x	x.x	x.xx
	xxxxxx	xxxxxxxxxx	xxxxx	xxxxxxx	x.xx	xxx	x	x.x	x.xx
				xxxxxxx	x.xx	xxx	x	x.x	x.xx
				xxxxxxx	x.xx	xxx	x	x.x	x.xx
				xxxxxxx	x.xx	xxx	x	x.x	x.xx

Source Listing: 16.2.9.1; Produced: yyyy-mm-ddThh:mm - Page x of y
H = Above Normal Range; Lo = Below Normal Range.

Programming Note: This table will be repeated for Part 2. Similar tables will be produced for Hematology Out of Normal Range Data - Part 1 and Part 2 (Table 14.3.2.2) and Urinalysis Out of Normal Range Data (Table 14.3.2.3).

OMO-103-01
Table 14.3.2.4
Autoimmune values - Part 1
Safety Set

<Parameter (<units>>						
Visit/ Time Point	n	Mean	SD	Min	Median	Max
SCREENING	x	x.xx	x.xxx	x.x	x.xx	x.x
CYCLE 3 DAY 01	x	x.xx	x.xxx	x.x	x.xx	x.x
CYCLE 4 DAY 01	x	x.xx	x.xxx	x.x	x.xx	x.x
...						

Source Listing: Listing 16.2.9.5; Produced: yyyy-mm-ddThh:mm - Page x of y

Programming Note: This table will be repeated for Part 2.

OMO-103-01
Table 14.3.2.5
Frequency of Autoimmune values - Part 1
Safety Set

<Parameter (<units>>		COHORT 1 (Dose xx mg/ml) (N=x)	Overall (N=x)
SCREENING	N	x (x.x)		x (x.x)
	Positive	x (x.x)		x (x.x)
	Negative	x (x.x)		x (x.x)
CYCLE 3 DAY 01	N	x (x.x)		x (x.x)
	Positive	x (x.x)		x (x.x)
	Negative	x (x.x)		x (x.x)
CYCLE 4 DAY 01	N	x (x.x)		x (x.x)
	Positive	x (x.x)		x (x.x)
	Negative	x (x.x)		x (x.x)

Source Listing: 16.2.9.5; Produced: yyyy-mm-ddThh:mm - Page x of y

Programming note: A similar table will be presented for Part 2

OMO-103-01
Table 14.3.3.1
Summary of 12-Lead ECG Data - Part 1
Safety Set

Visit/ Time Point		COHORT 1 (Dose xx mg/ml) (N=x)	Overall (N=x)
SCREENING	N	x (x.x)		x (x.x)
	Normal	x (x.x)		x (x.x)
	Abnormal NCS	x (x.x)		x (x.x)
	Abnormal CS	x (x.x)		x (x.x)
TREATMENT PERIOD	N	x (x.x)		x (x.x)
	Normal	x (x.x)		x (x.x)
	Abnormal NCS	x (x.x)		x (x.x)
	Abnormal CS	x (x.x)		x (x.x)
FOLLOW-UP PERIOD	N	x (x.x)		x (x.x)
	Normal	x (x.x)		x (x.x)
	Abnormal NCS	x (x.x)		x (x.x)
	Abnormal CS	x (x.x)		x (x.x)

Source Listing: 16.2.12.1; Produced: yyyy-mm-ddThh:mm - Page x of y

Programming note: A similar table will be presented for Part 2

OMO-103-01
Table 14.3.4.1

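### No planned summary table identifies new autoantibody positivity on OMO-103: the by-visit counts mix conversion, pre-existing positivity and dropout

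*SAP*

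**What the plan says.** The protocol synopsis names autoimmunity among the safety parameters. SAP 9.2.1 gives the panel as ANA, anti-thyroglobulin, RF and ASMA. The flow charts in SAP 3.3.1 and 3.3.2 schedule it at Screening, on treatment from Cycle 2 onwards, and at End of Treatment.

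Two tables report it. Table 14.3.2.5, "Frequency of Autoimmune values - Part 1", has N, Positive and Negative rows at Screening, Cycle 3 Day 1 and Cycle 4 Day 1, by cohort and overall. Table 14.3.2.4 gives n, mean, SD, minimum, median and maximum by visit, with no cohort columns. Both cite Listing 16.2.9.5 (Other Laboratory Data) as their source, and both are to be repeated for Part 2.

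The shell of Table 14.3.2.5 states no denominator, so the default in SAP 10.1 applies: "Unless otherwise specified, the denominator for each percentage will be the number of non-missing observations". The protocol synopsis agrees: "number and percent (of non-missing values) per category for categorical data". SAP 10.4 adds: "No methods to account for missing safety data will be used".

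SAP 11.5.2 describes listings only and does not define conversion. It also says "If there are no further parameters databased other than those specified in section 9.2.1 then the 'Other Laboratory Data' listings should display" a message that there is nothing to report.

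For ADA, SAP section 2 has this secondary objective in both Parts: "To assess the development of human anti-drug antibodies (ADA) to OMO-103". The only ADA output is Listing 16.2.9.4, "Summary of Anti-drug antibodies (ADA) to OMO-103".

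**The concern.** The safety question is whether patients who were autoantibody-negative become positive on OMO-103. Answering it needs each patient's Screening result set against that patient's later results. Neither autoimmune table does this. The percentage at a later visit can rise because negatives left, or stay flat while new positives replace positives who left. A reader could see a signal that is not there or miss one that is.

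The SAP compares patients with themselves elsewhere: the vital-signs shell includes change from baseline, and the ECG text in 11.5.4 plans a shift table. The autoimmune panel has neither.

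The missing End of Treatment row adds to this. As drawn, a patient who stops before Cycle 3 Day 1 contributes a Screening result to Table 14.3.2.5 and no post-dose result, even though an End of Treatment sample is scheduled.

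**Working it through.** The documents give no positivity or conversion rate, so there is no planned figure to reproduce. The check is whether the entries in Table 14.3.2.5 determine the number of new conversions.

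**Inputs.** Group size is 18 (the planned size of each Part 2 group). The following are assumed for illustration: 6 positive at Screening, 9 tested at Cycle 3 Day 1, and 4 of those positive. On the non-missing denominator the table would show 6/18 = 33.3% and then 4/9 = 44.4%.

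**Formula.** Let k be the number of Screening-positives among the 9 tested. If nobody reverts to negative, new conversions = 4 − k and baseline-negatives tested = 9 − k. With 12 Screening-negatives, the lower limit for k is max(0, 9 − 12) = 0. The upper limit is min(6, 4) = 4.

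| k | baseline-negatives tested | new conversions | rate |
|---|---|---|---|
| 0 | 9 | 4 | 44.4% |
| 1 | 8 | 3 | 37.5% |
| 2 | 7 | 2 | 28.6% |
| 3 | 6 | 1 | 16.7% |
| 4 | 5 | 0 | 0% |

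All five rows produce the same table entries. Allowing reversion does not change the range: with four positives in all, conversions still lie between 0 and 4.

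**How likely is the upper end?** If dropout is unrelated to Screening status, the chance that none of the 6 Screening-positives is among the 9 tested is C(12,9)/C(18,9) = 220/48,620 = 0.45%. The patterns k = 2, 3 and 4 have 15×792 + 20×924 + 15×792 = 42,240 of 48,620 combinations, or 86.9%. These are chances before the Cycle 3 result is seen. Even these common patterns span 0 to 2 conversions.

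**Other assumed counts.** With 3/18 positive at Screening and 3 positive at Cycle 3, the range is 0 to 3 conversions whether 9, 12 or 15 are tested. If all 18 are tested and nobody reverts, the answer is exactly 0. If reversion is allowed, it is again 0 to 3.

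**Other denominator.** The N row in the shell also carries a percentage, which would always be 100% under the non-missing rule, so the column N may be intended. The Cycle 3 figure would then be 4/18 = 22.2%, a fall from 33.3%, and it would still fit 0 to 4 new conversions. The gap does not depend on which denominator is meant.

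**What the range leaves out.** It covers only the nine tested. A conversion found in the End of Treatment sample of a patient who had already stopped is not in the table as drawn.

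**Source listing.** Both autoimmune tables cite Listing 16.2.9.5. Read literally, 11.5.2 fills that listing only with parameters outside 9.2.1, and the autoimmunity panel is inside 9.2.1. But SAP 10.1 requires all collected data to be listed, and 11.5.2 itself requires a listing of all safety laboratory data. These statements need to be reconciled.

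**The case against.** The strongest objection is that nothing is lost. SAP 10.1 requires all data in listings, with each subject's derived baseline, and Table 14.3.2.5 shows the Screening row and the N at every visit. In about 78 patients, conversions can be counted by hand. In Part 1, where the first two cohorts have one evaluable patient each and the rest follow a 3+3 scheme, the listing nearly serves as the shift table. Section 15 also allows layouts to change. This stands against the reading that conversion cannot be determined at all, and the documents do not support that reading. It does not supply a pre-specified definition of new positivity, so that would be settled after the data are seen.

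Three other inferences also go too far.

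- A reader might expect Listing 16.2.9.5 to come out empty. The tables' own citation and the all-data rule show that the panel is meant to appear there, so this is a wording conflict.
- A reader might say that ADA development goes unanalysed. The protocol synopsis classes ADA as a PD parameter, and SAP 14.5 says the contractor performs no PD analysis, so a separate analysis is possible. The documents do not describe one.
- A reader might conclude that autoantibody-positive patients will be enrolled. NSCLC patients must have "progressed after a chemotherapy and immunotherapy regimen", which makes Screening positives plausible. But SAP 3.2 places the full criteria in protocol sections 10.2 and 10.3, which were not available for this review, and the synopsis cannot show what they exclude.

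The illustration uses assumed counts and a Part 2 group size, and its upper extreme is improbable under unrelated dropout. That limits how large the problem is likely to be. It does not make the count identifiable from the table.

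**Conclusion.** The point holds as a gap in the planned summaries. No table in the SAP identifies new autoantibody positivity, and a change in percent positive in Table 14.3.2.5 cannot be read as conversion. On the assumed counts, one set of entries fits 0 to 4 new conversions, or 0 to 2 under the dropout patterns most likely if leaving is unrelated to status. The actual size depends on Screening positivity and attrition, and the documents give neither.

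The conclusion assumes that some patients are positive at Screening, and that either some are not retested or some revert. With no Screening positives, a later positive count is a count of converters, and with full retesting and no reversion the table would be adequate. Autoimmunity is a named safety parameter in a first-in-human study and the remedy is cheap, so the sponsor should make the change. For ADA, the supportable conclusion is narrower: this SAP lists a secondary objective without summarising it and does not say where else it is analysed.

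**What to change.** 1. Define a treatment-emergent positive in SAP 11.5.2, and supplement Table 14.3.2.5 with a shift table from Screening to any post-dose positive, including End of Treatment. Present it per marker, by cohort in Part 1 and by tumour group in Part 2. Give n (%) newly positive among baseline-negatives with at least one post-dose sample, and show baseline-positives separately.
2. If the by-visit table is kept, add an End of Treatment row and a denominator footnote.
3. Reword 11.5.2 so that panels in 9.2.1 without their own listing, including autoimmunity, go into Listing 16.2.9.5. In the same edit, correct the shell note that gives number 16.2.9.4 to other laboratory data, since the listing index gives it to ADA.
4. For ADA, add the matching table (pre-existing, treatment-emergent, negative) for both Parts, or, if the PD exclusion in 14.5 is meant to cover ADA, state where the objective is analysed.

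The cost is SAP and shell wording plus one or two tables. All the samples, including Screening, are already scheduled.

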16 APPENDICES

16.1 NORMAL RANGES

Vital Sign Parameters		
Parameter	Normal Range	Unit
Pulse Rate	40 - 100	Beats per minute (bpm)
Systolic Blood Pressure	90 – 140	mmHg
Diastolic Blood Pressure	50 - 90	mmHg
Respiratory Rate	12 - 18	Breaths per minute
Temperature	35.0 - 37.5	Degrees Celsius

ECG Parameters		
Parameter	Normal Range	Unit
Heart Rate	40 - 100	Beats per minute (bpm)
PR Interval	120 – 220	Millisecond (msec)
QRS Width	70 – 120	Millisecond (msec)
QT Interval	N/A	Millisecond (msec)
QTc Interval (Bazett's & Fridericia's formulae)	350 – 450 (males) 350 – 450 (females)	Millisecond (msec) Millisecond (msec)
